**17.2 If applicable, provide a power analysis.**

*NOTE: This may not apply to certain types of studies, including chart/records reviews, survey studies, or observational studies. This question is asked to elicit*

*whether the investigator has an adequate sample size to achieve the study objectives and justify a conclusion.*

Response: N/A

*17.3 Describe any procedures that will be used for quality control of collected data.*

Response: N/A

## **18.0 Confidentiality**

### **A. Confidentiality of Study Data**

*Describe the local procedures for maintenance of confidentiality of **study data** and any records that will be reviewed for data collection.*

*18.1 A. Where and how will all data and records be stored? Include information about: password protection, encryption, physical controls, authorization of access, and separation of identifiers and data, as applicable. Include physical (e.g. paper) **and** electronic files.*

Response: Electronic records will be managed in the REDCap system. Physical documents will be secured in University at Buffalo – South Campus, [name]. Data may be extracted by UB's CTSI office for analysis following completion of collection and stored securely by that office.

Commented [RJ47]: Please respond to this section.

*18.2 A. How long will the data be stored?*

Response: Data will be stored until June 1, 2020.

*18.3 A. Who will have access to the data?*

Response: The Principal Investigator, Study Advisor, and analysts assigned by UB's CTSI office will have access to this data.

*18.4 A. Who is responsible for receipt or transmission of the data?*

Response: The data will be received by utilizing the REDCap system.

*18.5 A. How will the data be transported?*

Response: Electronic data will be collected through REDCap.

## B. Confidentiality of Study Specimens

*Describe the local procedures for maintenance of confidentiality of study specimens.*

**N/A:** No specimens will be collected or analyzed in this research.  
(Skip to Section 19.0)

*18.6 B. Where and how will all specimens be stored? Include information about: physical controls, authorization of access, and labeling of specimens, as applicable.*

Response:

*18.7 B. How long will the specimens be stored?*

Response:

*18.8 B. Who will have access to the specimens?*

Response:

*18.9 B. Who is responsible for receipt or transmission of the specimens?*

Response:

*18.10 B. How will the specimens be transported?*

Response:

## 19.0 Provisions to Monitor the Data to Ensure the Safety of Subjects

**N/A:** This study is not enrolling subjects, or is limited to records review procedures only. This section does not apply.

*NOTE: Minimal risk studies may be required to monitor subject safety if the research procedures include procedures that present unique risks to subjects that require monitoring. Some examples include: exercising to exertion, or instruments that elicit suicidality or substance abuse behavior. In such cases, N/A is not an acceptable response.*

*19.1 Describe the plan to periodically evaluate the data collected regarding both harms and benefits to determine whether subjects remain safe.*

Response: [N/A: This is a minimal risk study that does not pose any anticipated harm to participants.](#)

19.2 *Describe what data are reviewed, including safety data, untoward events, and efficacy data.*

Response: [N/A](#)

19.3 *Describe any safety endpoints.*

Response: [N/A](#)

19.4 *Describe how the safety information will be collected (e.g., with case report forms, at study visits, by telephone calls with participants).*

Response: [N/A](#)

19.5 *Describe the frequency of safety data collection.*

Response: [N/A](#)

19.6 *Describe who will review the safety data.*

Response: [N/A](#)

19.7 *Describe the frequency or periodicity of review of cumulative safety data.*

Response: [N/A](#)

19.8 *Describe the statistical tests for analyzing the safety data to determine whether harm is occurring.*

Response: [N/A](#)

19.9 *Describe any conditions that trigger an immediate suspension of the research.*

Response: [N/A](#)

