## 6.0 Inclusion and Exclusion Criteria

6.1 *Describe the criteria that define who will be **included** in your final study sample.*

*NOTE: This may be done in bullet point fashion.*

Response:

- Adults, age 18 and above, self-reporting bothersome tinnitus lasting longer than three months.
- Have been evaluated by an audiologist or otologist.
- Those willing and able to utilize their own smart device or computer meeting the following requirements.

**Commented [RJ9]:** Over 18?

**Commented [RJ10]:** You may want to only include individuals with a smart phone or internet access.

- For Mac: Requires iOS 10.0 or later. Compatible with iPhone, iPad, and iPod touch.
- For Android: varies by device.
- Data and/or Wi-Fi access

6.2 *Describe the criteria that define who will be **excluded** from your final study sample.*

*NOTE: This may be done in bullet point fashion.*

Response:

- Individuals with meditation training or consistent meditation practice (practice that totals more than 20 minutes daily) within the past six months.
- Those indicated by the Hospital Anxiety and Depression Scale to have “abnormal” indications for anxiety or depression.
- Those with any conditions that would restrict them from being able to either sit, walk, or lie down for at least 30 minutes at a time.

6.3 *Indicate specifically whether you will include any of the following special populations in your study using the checkboxes below.*

*NOTE: Members of special populations may not be targeted for enrollment in your study unless you indicate this in your inclusion criteria.*

Response:

- Adults unable to consent
- Individuals who are not yet adults (infants, children, teenagers)
- Pregnant women
- Prisoners

6.4 *Indicate whether you will include non-English speaking individuals in your study. **Provide justification if you will exclude non-English speaking individuals.***

*In order to meet one of the primary ethical principles of equitable selection of subjects, non-English speaking individuals may **not** be routinely excluded from research as a matter of convenience.*

*In cases where the research is of therapeutic intent or is designed to investigate areas that would necessarily require certain populations who may not speak English, the researcher is required to make efforts to recruit and include non-English speaking individuals. However, there are studies*

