Subjects will begin their meditation practice at home using suggested guided meditations. Subjects will be asked to create an account on the meditation website InsightTimer. This website has an accompanying smart device application that allows users to access guided meditations and timed sessions. With an account, users' session data is logged. Subjects will be encouraged to use guided meditations of their choice or timed meditation using the InsightTimer. They will be asked to practice a half hour, five days per week for eight weeks. Subjects must complete at least one hour per week to remain in the study. Every week during the study, subjects will be asked to submit their data from the application into REDCap. Subjects will have the PI's email and a phone number for technical assistance.

Subjects' meditation practice will last for eight weeks with measures being utilized after week three and week eight. The following measures will be sent to participants by email and submitted through REDCap.

- Tinnitus Handicap Questionnaire
- Tinnitus Handicap Inventory
- Tinnitus Functional Index
- Hospital Anxiety and Depression Scale
- Mindful Attention Awareness Scale

← **Commented [RJ25]:** What technology is needed?

**Commented [RJ26]:** What application? Please describe the requirement here in further detail.

**Commented [BF27R26]:** I hope this is clearer now.

← **Formatted:** Bulleted + Level: 1 + Aligned at: 0.75" + Indent at: 1"

**Commented [RJ28]:** You describe above participation for 3 weeks. Are there additional research procedures or activities that are required up to 8 weeks?

**Commented [BF29R28]:** My language was unclear. The intervention lasts 8 weeks with measures after weeks 3 and 8.

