## 10.2 Describe what data will be collected.

*NOTE: For studies with multiple data collection points or long-term follow up, consider the addition of a schedule or table in your response.*

Response:

- [Each week, participants will enter the amount of time spent meditating on a form through REDCap.](#)
- [Before week 1:](#)
  - [Tinnitus Handicap Questionnaire](#)
  - [Tinnitus Handicap Inventory](#)
  - [Tinnitus Functional Index](#)
  - [Hospital Anxiety and Depression Scale](#)
  - [Mindful Attention Awareness Scale](#)
  - [University at Buffalo Tinnitus Intake Questionnaire](#)
- [After week 3:](#)
  - [Tinnitus Handicap Questionnaire](#)
  - [Tinnitus Handicap Inventory](#)
  - [Tinnitus Functional Index](#)
  - [Hospital Anxiety and Depression Scale](#)
  - [Mindful Attention Awareness Scale](#)
- [After week 8:](#)
  - [Tinnitus Handicap Questionnaire](#)
  - [Tinnitus Handicap Inventory](#)
  - [Tinnitus Functional Index](#)
  - [Hospital Anxiety and Depression Scale](#)
  - [Mindful Attention Awareness Scale](#)

 10.3 List any instruments or measurement tools used to collect data (e.g. questionnaire, interview guide, validated instrument, data collection form).

*Include copies of these documents with your submission.*

Response:

- [Tinnitus Handicap Questionnaire](#)
- [Tinnitus Handicap Inventory](#)
- [Tinnitus Functional Index](#)

- Hospital Anxiety and Depression Scale
- Mindful Attention Awareness Scale
- University at Buffalo Tinnitus Intake Questionnaire

**Commented [BF30]:** [https://drive.google.com/open?id=104a3hbqsAAkvfesLVLFQCv168M2\\_RYQa](https://drive.google.com/open?id=104a3hbqsAAkvfesLVLFQCv168M2_RYQa)

10.4 *Describe any source records that will be used to collect data about subjects (e.g. school records, electronic medical records).*

Response: No additional records will be requested or gathered from subjects.

10.5 *Indicate whether or not **individual** subject results, such as results of investigational diagnostic tests, genetic tests, or incidental findings will be shared with subjects or others (e.g., the subject's primary care physician) and if so, describe how these will be shared.*

Response: Individual subject results will not be shared with any other parties.

10.6 *Indicate whether or not **study** results will be shared with subjects or others, and if so, describe how these will be shared.*

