**Describe other resources available to conduct the research.**

14.2 *Describe the time and effort that the Principal Investigator and research staff will devote to conducting and completing the research.*

*NOTE: Examples include the percentage of Full Time Equivalents (FTE), hours per week. The question will elicit whether there are appropriate resources to conduct the research.*

**Response:** The PI will dedicate 6-12 hours weekly to this study. The PI and study advisor that are assigned to this study will be able to devote sufficient time to the procedures in adherence with the protocol.

**Commented [38]:** Again, not sure on the exact language to describe the specifics of who does what.

14.3 *Describe the availability of medical or psychological resources that subjects might need as a result of anticipated consequences of the human research, if applicable.*

*NOTE: One example includes: on-call availability of a counselor or psychologist for a study that screens subjects for depression.*

**Response:** Potential subjects scoring “abnormal” on the Hospital Anxiety and Depression Scale will be referred to area mental health services.

**Commented [RJ39]:** You can state 3 hours a week or .5 FTEs. Whatever you and your research team can devote to conducting this study (example below).

“The PI, study coordinator, or other study staff that are assigned to this study and will be able to devote sufficient time to the procedures in adherence with the protocol.”

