## 21.0 Risks to Subjects

21.1 *List the reasonably foreseeable risks, discomforts, hazards, or inconveniences to the subjects related to their participation in the research. Consider physical, psychological, social, legal, and economic risks. Include a description of the probability, magnitude, duration, and reversibility of the risks.*

*NOTE: Breach of confidentiality is always a risk for identifiable subject data.*

Commented [RJ49]: Please respond to this section.

Response: Subjects will be asked to be seated and still for long periods of time. Some subjects may experience minor physical discomfort. There may also be an increased risk for circulation to be reduced due to subjects being in one position for an extended period of time.

21.2 *Describe procedures performed to lessen the probability or magnitude of risks, including procedures being performed to monitor subjects for safety.*

Response: To reduce discomfort and poor circulation that can occur in seated meditation, subjects will also be instructed to participate in lying or walking meditation.

21.3 *If applicable, indicate which procedures may have risks to the subjects that are currently unforeseeable.*

Response: N/A

21.4 *If applicable, indicate which research procedures may have risks to an embryo or fetus should the subject be or become pregnant.*

Response: N/A

21.5 *If applicable, describe risks to others who are not subjects.*

Response: N/A

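### Section 19 is answered N/A on a no-harm statement that conflicts with Section 21.1, and the protocol plans no in-study review or handling of the HADS scores that enrolled subjects give after weeks 3 and 8 and on removal

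*Protocol*

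**What the plan says.** **Safety monitoring.** Section 19.1 is answered N/A with the reason "This is a minimal risk study that does not pose any anticipated harm to participants". Items 19.2 to 19.9 are then each answered N/A. They cover the data reviewed, safety endpoints, how and how often safety information is collected, the reviewer (the prompt reads "Describe who will review the safety data"), the frequency of cumulative review, statistical tests and triggers for suspension.

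**Foreseeable risks.** Section 21.1 names minor physical discomfort from sitting still and adds: "There may also be an increased risk for circulation to be reduced due to subjects being in one position". Section 21.2 offers lying or walking meditation as mitigation and describes no monitoring.

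**HADS before enrolment.** Section 6.2 excludes "Those indicated by the Hospital Anxiety and Depression Scale to have “abnormal” indications for anxiety or depression". Section 14.3 states: "Potential subjects scoring “abnormal” on the Hospital Anxiety and Depression Scale will be referred to area mental health services".

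**HADS after enrolment.** Section 10.1 describes "measures being utilized after week three and week eight", and the HADS is on that list. Section 10.2 schedules the "Hospital Anxiety and Depression Scale" before week 1, after week 3 and after week 8. Section 20.2 asks subjects who are removed to complete it again.

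**The concern.** There are two separate problems.

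First, the reason given for leaving all of Section 19 as N/A does not agree with the protocol's own list of risks. If Section 19 is followed as written, the two discomforts that Section 21.1 foresees are never asked about, so the study could not say how many subjects had them.

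Second, the protocol treats an abnormal HADS as a result that needs action at entry: it excludes the person and leads to a referral. Once a subject is enrolled, the same instrument is given again and the protocol says nothing about the result. With the N/A answers to 19.2 and 19.4 to 19.7, nobody is assigned to look at those scores while the subject is still in the study. A subject whose score became abnormal by week 3 could continue to week 8 without any planned look at that score.

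**Working it through.** The plan states no figure to reproduce, and the point is one of consistency and coverage. The check sets the sections side by side.

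**Step 1: the reason for N/A against the listed risks.**
- Section 19.1: no harm anticipated, so no monitoring plan.
- Section 21.1: two physical risks, entered in answer to a prompt for foreseeable risks.
- Section 21.2: mitigation only, although the prompt also asks about monitoring subjects for safety.

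The statement in 19.1 and the list in 21.1 cannot both stand as worded. The conflict is limited to physical risks; Section 21 names no psychological one.

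**Step 2: are the listed discomforts captured anywhere?** The weekly REDCap entry in Section 10.2 asks for time spent meditating. The instruments in Section 10.3 are tinnitus, mood and mindfulness questionnaires. The contact route in Section 10.1 is described as technical assistance. Items 19.4 and 19.5 are N/A. The protocol therefore provides no collection of the 21.1 discomforts.

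**Step 3: HADS by time point, and what the protocol says follows.**

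| Time point | Source | Stated handling of an abnormal score |
|---|---|---|
| Entry | 6.2, 14.3 | Exclusion; referral of potential subjects |
| Before week 1, after consent | 10.1, 10.2 | Possibly covered by 14.3 (see below) |
| After week 3 | 10.1, 10.2 | None |
| After week 8 | 10.1, 10.2 | None |
| On removal | 20.2 | None |

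The before-week-1 row is unclear. The first HADS round visible in the text comes after consent, and the screening form mentioned in Section 8.1 is an attachment that is not shown. The exclusion and the 14.3 referral may therefore operate on that round. The clear gap is week 3, week 8 and removal.

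**Step 4: does another section fill the gap?** The withdrawal reasons in Section 20.1 concern late data, late surveys and too little meditation; none concerns worsening. Section 20.3 says how data from withdrawn subjects are analysed, not whether anyone reads them at the time. Section 18.1 says the institution's analysis office may extract data once collection is complete. Section 18.3 gives the investigator and advisor access to the data but assigns no review.

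**Step 5: scale.** The target in Section 5.1 is 30 subjects, and two follow-up rounds are scheduled: 30 × 2 = 60 HADS forms. This assumes that the target is met exactly and every form is completed. Section 5.1 allows more or fewer subjects, dropout would lower the count, and forms completed on removal would be additional. The documents give no rate at which enrolled subjects might become abnormal, so no expected number is offered.

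**The case against.** The strongest reply is that this is a minimal-risk meditation study and the template does not forbid N/A. Its note says only that "Minimal risk studies may be required to monitor subject safety if the research procedures include procedures that present unique risks to subjects that require monitoring", and the protocol does not describe sitting still or completing the HADS as such a procedure. That stands: N/A is not barred as such. What fails is the reason given for it, because Section 21.1 contradicts that reason.

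A reader might also infer that worsening would go unrecorded, or that the study could not count subjects who worsened. The documents do not support this. The HADS and the tinnitus scales are collected at baseline, week 3 and week 8 and requested on removal, Section 2.1 names the HADS as an outcome measure, and Section 20.3 keeps the data of subjects who withdraw. A count of worsened scores is possible from what is collected. Only the physical discomforts lack a form.

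Nor can one say that the scores would go unread. The investigator runs all aspects of the study and corresponds weekly with the advisor (Section 14.4), and both have data access. Either could look. The supportable statement is that no review is planned or assigned.

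It is also fair to say that the conflict with Section 21.1 does not show that low mood is an anticipated harm. The HADS point stands on its own, on the contrast between Section 14.3 and the repeat schedule.

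Finally, consent pages and attachments are not shown and may give subjects a contact for problems. It therefore cannot be asserted that harms would go unreported. Such a contact would still leave Sections 14.3, 19 and 21.1 unreconciled.

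**Conclusion.** The point holds in two limited parts. The no-harm reason in Section 19.1 conflicts with Section 21.1, and the protocol provides no collection of the discomforts it foresees. The protocol also states no handling, and plans no in-study review, of the HADS in enrolled subjects after week 3, after week 8 and on removal: up to 60 scheduled follow-up forms at 30 subjects with full completion, plus any completed on removal.

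This is more than omitted detail. The protocol was asked what is reviewed, how, when and by whom, and answered N/A each time. These are protocol matters that a statistical analysis plan would not normally settle. The harms listed are physical, the discomfort is called minor and the study is small, so this is a correction that should be made and not a reason to doubt the design. The conclusion rests on the protocol text alone and on no assumed event rate.

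**What to change.** 1. Reconcile Sections 10.2, 14.3, 19.1 to 19.9, 20.2 and 21.1 so that the protocol says one consistent thing about follow-up and exit HADS results in enrolled subjects. Which rule applies is for the investigator and the IRB.
2. Bring the reason in Section 19.1 into line with the risks in Section 21.1.
3. Replace the N/A in Sections 19.2 to 19.7 with the scores already collected, the existing study role that reviews them, and when.
4. Add one item on the Section 21.1 discomforts to the weekly REDCap form.
5. Report the number of subjects whose scores worsened and the number with discomfort. State alongside that, without a control arm, these counts do not show that meditation caused the change.

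The cost is protocol wording, one REDCap item and a short look at each form, within the 6 to 12 hours a week that the investigator already commits in Section 14.2. The downside is slightly more work for the investigator and the subjects. No extra staff are needed.

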## 20.0      Withdrawal of Subjects

**N/A:** This study is not enrolling subjects. This section does not apply.

Commented [RJ48]: Please respond to this section.

20.1 *Describe anticipated circumstances under which subjects may be withdrawn from the research without their consent.*

Response: Subjects may be withdrawn for the following reasons:

- Failure to submit mediation data in a timely manner.
- Failure to complete surveys and questionnaires in a timely manner.
- Failure to comply to participating in the intervention. Subjects practicing meditation less than one hour per week may be withdrawn from the study.

20.2 *Describe any procedures for orderly termination.*

*NOTE: Examples may include return of study drug, exit interview with clinician. Include whether additional follow up is recommended for safety reasons for physical or emotional health.*

Response: Participants will be informed of their removal from the study and asked to complete questionnaires (Tinnitus Handicap Questionnaire, Tinnitus Handicap Inventory, Tinnitus Functional Index, Hospital Anxiety and Depression Scale, Mindful Attention Awareness Scale) via the REDCap system. This intervention poses low risk from discontinuing abruptly.

20.3 *Describe procedures that will be followed when subjects withdraw from the research, including retention of already collected data, and partial withdrawal from procedures with continued data collection, as applicable.*

Response: Data already collected from subjects who withdraw will be analyzed up to the point of their last completed questionnaires.

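### Late reporting alone can end a subject's data collection, and nothing keeps a removed subject in follow-up to the week-8 outcome

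*Protocol*

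**What the plan says.** Protocol section 20.1 opens its list with "Subjects may be withdrawn for the following reasons" and gives three grounds. Two concern reporting only: "Failure to submit mediation data in a timely manner" and "Failure to complete surveys and questionnaires in a timely manner". The third concerns practice itself: "Subjects practicing meditation less than one hour per week may be withdrawn from the study". Section 20.1 does not say what counts as timely, how many misses matter, or whether a reminder comes first.

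Section 20.2 sets out what follows removal: "Participants will be informed of their removal from the study and asked to complete questionnaires". The five instruments it lists are those repeated at the scheduled follow-ups. Section 20.3 keeps data already collected and analyses them as far as the last completed questionnaires.

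The reporting load is in section 10.1. For the logs: "Every week during the study, subjects will be asked to submit their data from the application into REDCap". For the questionnaires: "Subjects' meditation practice will last for eight weeks with measures being utilized after week three and week eight". Section 2.1 defines the outcome as bother measured before, during and after the 8-week period. Section 5.1 targets 30 subjects, and section 4.1 describes a non-randomized interventional study.

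**The concern.** A late form and a stopped intervention are different events. Someone who logs a week late, or returns the week-3 set late, may be practising as asked and quite able to answer at week 8. Treating lateness as a ground for removal can turn a small defect, in one log or in the intermediate measurement, into loss of the final one.

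This matters for two reasons. First, the hypothesis in section 1.2 relates reduction in bother to time spent meditating. Prompt reporting plausibly goes with engagement, and engagement is close to that exposure. Removing late reporters could select subjects on something correlated with the exposure and narrow its range. With no comparison arm, the data would offer little to reveal this. Second, with about 30 subjects each lost week-8 value is a noticeable share (1/30 = 3.3%), and the paired t-test named in section 17.1 needs both members of a before/week-8 pair.

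**Working it through.** The protocol gives no dropout rate, and section 17.2 answers the power-analysis question as not applicable, so there is no planned figure to reproduce. The check has two parts.

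**1. What happens to a subject removed for lateness**

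| Step | Section | Result |
|---|---|---|
| Subject is still meditating but a log or questionnaire is late | 20.1, first two grounds | Removal permitted; practice time is a separate ground |
| Subject is removed | 20.2 | Five questionnaires requested at removal, whenever that is |
| Week 8 arrives | 10.1, 10.2, 20.2, 20.3 | No section provides for sending the set to a removed subject |
| Data are used | 20.3 | Retained up to the last completed set |

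A subject removed after, say, week 4 supplies at best an exit score from about that time. It is a post-baseline value, but not the 8-week outcome of section 2.1.

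**2. How many subjects the discretion could reach (illustration)**

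Deadlines before the week-8 questionnaires, counted from section 10.1:

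- Seven weekly logs (weeks 1 to 7) plus the week-3 set: 7 + 1 = 8. These are strictly earlier than week 8.
- Counting the eighth log too, which falls due at about the same time as the week-8 set: 8 + 1 = 9.

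If each of *k* deadlines is missed independently with probability *p*, the chance of at least one miss is 1 − (1 − *p*)^*k*. The values of *p* are assumptions; the protocol gives none.

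| *k* | *p* | Calculation | Share with at least one miss | Of 30 subjects |
|---|---|---|---|---|
| 8 | 2% | 1 − 0.98^8 | 14.9% | 4.5 |
| 8 | 5% | 1 − 0.95^8 | 33.7% | 10.1 |
| 9 | 2% | 1 − 0.98^9 | 16.6% | 5.0 |
| 9 | 5% | 1 − 0.95^9 | 37.0% | 11.1 |

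Widening *p* to 1%–10% gives 7.7% to 57.0% for *k* = 8 and 8.6% to 61.3% for *k* = 9.

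Independence pushes these shares up. In the opposite extreme, where the same people miss every deadline, the share with any miss is simply *p*: 2% to 5%, or 30 × 0.02 = 0.6 to 30 × 0.05 = 1.5 subjects. Real behaviour probably lies between the two. In every case the figure counts subjects to whom the discretion could be applied, not subjects who would be withdrawn.

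**The case against.** The best defence is that section 20.1 reserves a discretion and sets no trigger. It answers a template prompt about anticipated circumstances and says subjects *may* be withdrawn. Section 10.1 uses mandatory wording for the weekly practice minimum, but none for reporting. That stands: a reader might infer that one missed deadline removes a subject, and the text does not say so. Nor does it exclude it, since no number of misses is given.

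A reader might also see a contradiction in asking someone removed for not completing questionnaires to complete the same ones. There is none. Section 20.1 concerns timeliness, and the request in section 20.2 is a last attempt to recover data. It softens the loss, because a removed subject can still give a value on each repeated measure. But the value comes at a variable time, and someone removed for late questionnaires may not return it.

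Similarly, section 20.3 might be read as discarding the exit set. It is a retention rule, and nothing in it bars an exit set that was completed. How such values enter the analysis may properly be left to an analysis plan. Whether the week-8 set is sent at all is a matter of study conduct, and that belongs in the protocol.

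Timeliness has some value for data quality too. Subjects enter the exposure themselves, and a week-3 set returned at week 6 is not a week-3 measurement. It would be wrong to say the rule gains nothing. But the gain comes from knowing when a form was completed, which does not require removing the person. Section 10.1 also says the app logs sessions under the user's account, so a late weekly total need not rest on memory.

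Finally, the investigator needs a way to close out a subject who has gone silent. That is fair, and sending one further questionnaire link at week 8 does not prevent it.

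**Conclusion.** The point holds in limited form. The protocol lets the investigator withdraw subjects solely for late logs or late questionnaires, without a stated threshold, even if they are still meditating, and it provides no week-8 assessment after removal. The final outcome can be lost for a reason that may be related to engagement.

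A reader might go further and infer that late reporters benefit less, so that the before-after change is inflated. The protocol contains nothing on how late reporters fare, so neither the direction nor the size of a bias can be stated. The illustrative 15% to 37% exposed rests on assumed miss rates of 2% to 5%, on independence, and on a count of eight or nine deadlines. No withdrawal rate can be derived from the document.

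The change is still worth making. The potential loss is avoidable, it may be selective, and the study is small with one group.

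**What to change.** - **Section 20.1:** remove late meditation data and late questionnaires as grounds for ending data collection. The ground on practice time is outside this point.
- **Section 10.1:** state that late forms are accepted and that their completion date is recorded, so each set can be classed as on time or late. Automated reminders would help.
- **Sections 20.2 and 20.3:** state that the week-8 questionnaire set is sent at week 8 to every subject who has not withdrawn consent, whatever earlier form was late or missed, and that those data are included in the analysis. An exit set at removal can stay as an addition.

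The cost is a few lines of text and some reminder set-up. The instruments and the week-8 mailing are already planned. The downside is that some forms will be completed outside the intended week; the completion date identifies them, and the analysis can treat them accordingly.
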